[figure not shown]

Official Title:	Pembrolizumab in Treating Participants With Metastatic, Recurrent or Locally Advanced Cancer and Genomic Instability
NCT number:	NCT03428802
Document Type:	Protocol SAP
Date of the Document:	02/22/2023

3	5.1.3	19	#2 changed as “Has a diagnosis of immunodeficiency that consistently requires more than 10 mg daily of prednisone or equivalent or has resulted in life threatening episodes previously regardless of current treatment.”
4	5.1.3	20	#9 changed as “Has active autoimmune disease which currently requires disease modifying agents that include corticosteroids > 10 mg of prednisone or equivalent or immunosuppressive drugs. Replacement therapy (e.g., thyroxine, insulin, or physiologic corticosteroid replacement therapy for adrenal or pituitary insufficiency, etc.) is not considered a form of systemic treatment.”
5	5.1.3	20	#10 changed as “Has a history of (non-infectious) pneumonitis that required steroids or has current pneumonitis.”
6	5.1.3	21	#19 changed as “Has a known history of Hepatitis B (defined as Hepatitis B surface antigen [HBsAg] reactive) or known active Hepatitis C virus (defined as HCV RNA [qualitative] is detected) infection.”
7	5.1.3	21	“MSI unknown will be excluded” appended to exclusion criteria #18
8	6.1	34	Table footnote modified for clarity
9	11.5.1.1	69	Blood collection into Red Top tubes added
10	11.5.1.2	69	Minor text edits on tumor tissue handling
11	11.5.2.1	70	Processing of peripheral blood into Red Top tubes appended (bullet b)©
12	11.5.2.2; bullet (a)	71	Genetic analyses specified (next generation sequencing)
13	11.5.2.2; bullet (e)	72	‘RNA later’ replaced with ‘TRIzol’
14	11.5.2.2; Table 9	73	Text modifications
15	11.5.3; bullet (e)	73	Address change
16	11.5.4.4	76	Appended “nanosttring, single cell RNA-sequencing, exosome sequencing, multispecial immunostain”
17	2.1	10	Required number of slides updated to 15
			Modified to read: Patients will be evaluated for response by RECIST 1.1 and irRC criteria after every 9 weeks (3 cycles) of treatment until cycle 8, then subsequently after every 12 weeks (4 cycles) of treatment.
	6.1	37	Updated the schedule for collection of Circulating cell-free DNA
		38	Footnote #2 – added: All screening labs should be performed within 10 days of treatment initiation (refer to inclusion criteria #7, Table 1). Footnote #3 modified to read: “Prior to Cycles 4”
	7.1.2.6.2	43	Footnote #6 – added: every 6 weeks of treatment  Deleted: [name] PhD Added: [name], Managing Deleted: a flow cytometry multiplex assay (LegendPlex) detecting IL-2, IL-4, IL-10, IL-6, IL-17A, TNF- $\alpha$ , sFas, sFasL, IFN- $\gamma$ , granzyme A, granzyme

			
B, perforin and granulysin
 
Added: Luminex Multiplexe Analysis against a panel of 48 human cytokines/chemokines.
 
Moved (insertion)
 
44
 
Added: "Rutgers Cancer Institute of New Jersey (Sponsor) Office of Human Research Services via OnCore within 24 hours of site notification. The completed SAE report (signed by the Investigator) must be sent to the Rutgers CINJ OHRS QA department."
 
10.7
 
51
 
Deleted: Sites will contact the Rutgers Cancer Institute of New Jersey's OHRS Registration Desk [contact] and [contact] to register subjects.
 
11.5
 
63
 
Added: Sites will register and enroll patients through OnCore® the Clinical Trials Management System for this study.
 
Removed text from Sections 11.5, 11.5.1, 11.5.1.1, 11.5.1.2, 11.5.2, 11.5.2.1, 11.5.2.2, Table 9, 11.5.3, 11.5.4, 11.5.4.1, 11.5.4.2, 11.5.4.3, 11.5.4.4
 
Updated Section 11.5 with the biospecimen collection requirements and updated to include reference to the 051709 Correlative Research Laboratory Manual for collection, processing, and shipping details.

18	2.1		
Changed irRC to iRECIST

	4.1		
Deleted: Refer to the Investigator's Brochure (IB)/approved labeling for detailed background information on MK-3475.
 
Added: Pembrolizumab is a potent humanized immunoglobulin G4 (IgG4) monoclonal antibody (mAb) with high specificity of binding to the programmed cell death 1 (PD 1) receptor, thus inhibiting its interaction with programmed cell death ligand 1 (PD-L1) and programmed cell death ligand 2 (PD-L2). Based on preclinical in vitro data, pembrolizumab has high affinity and potent receptor blocking activity for PD 1. Pembrolizumab has an acceptable preclinical safety profile and is in clinical development as an intravenous (IV) immunotherapy for advanced malignancies. Keytruda® (pembrolizumab) is indicated for the treatment of patients across a number of indications because of its mechanism of action to bind the PD-1 receptor on the T cell. For more details on specific indications refer to the Investigator brochure (IB).

	4.2.1		
Deleted: entire section
 
Added: The planned dose of pembrolizumab for this study is 200 mg every 3 weeks (Q3W). Based on the totality of data generated in the Keytruda development program, 200 mg Q3W is the appropriate dose of pembrolizumab for adults across all indications and regardless of tumor type. As outlined below, this dose is justified by:
 
 
Clinical data from 8 randomized studies in melanoma and NSCLC indications demonstrating flat dose- and exposure-efficacy relationships from 2 mg/kg
 

		
Q3W to 10 mg/kg every 2 weeks ( Q2W), , representing an approximate 5- to 7.5-fold exposure range (refer to IB, Section 5.2.2)
 
 
• Population PK analysis showing that both fixed dosing and weight-based dosing provides similar control of PK variability with considerable overlap in the distributions of exposures, supporting suitability of 200 mg Q3W
 
• Clinical data showing meaningful improvement in benefit-risk including overall survival at 200 mg Q3W across multiple indications, and
 
• Pharmacology data showing full target saturation in both systemic circulation (inferred from pharmacokinetic [PK] data) and tumor (inferred from physiologically-based PK [PBPK] analysis) at 200 mg Q3W
 
 
Deleted: without transfusion or EPO dependency (within 7 days of assessment)
 
Added: without erythropoietin dependency and without packed red blood cell (pRBC) transfusion within last 2 weeks.
 
Changed <math>\geq 60</math> mL/min to <math>\geq 30</math> mL/min
 
Deleted Inclusion Criteria #10: Male subjects should agree to abstinence or use of an adequate method of contraception starting with the first dose of study therapy through 120 days after the last dose of study therapy.

	5.1.2	
	5.1.3	
Exclusion criteria #4 modified to read: Has severe hypersensitivity (<math>\geq</math>Grade 3) to pembrolizumab or any of its excipients.
 
Exclusion criteria #10 modified to read: Has a history of (non-infectious) pneumonitis/ interstitial lung disease that required steroids or has current pneumonitis/interstitial lung disease.
 
Deleted: or father children from exclusion criteria # 14.
 
Added to exclusion criteria #15: or with an agent directed to another stimulatory or co-inhibitory T-cell receptor (eg, CTLA-4, OX 40, CD137).
 
Deleted from exclusion criteria #17: Note: Seasonal influenza vaccines for injection are generally inactivated flu vaccines and are allowed; however intranasal influenza vaccines (e.g., Flu-Mist®) are live attenuated vaccines, and are not allowed
 
Exclusion criteria # 17 modified to read: Has received a live vaccine or live-attenuated vaccine within 30 days of planned start of study therapy. Administration of killed vaccines is allowed.

	5.2.1.1.	
Deleted: Details on preparation and administration of pembrolizumab (MK-3475) are provided in the Pharmacy Manual.

	5.2.1.2.	
Changed Section 5.2.1.2 heading to read: Dose Modification and toxicity management for immune-related AEs associated with pembrolizumab and combination therapy
 
Added: including coadministration with additional compounds,

		
Added: and may affect more than one body system simultaneously. Therefore, early recognition and initiation of treatment is critical to reduce complications. Based on existing clinical study data, most irAEs were reversible and could be managed with interruptions of pembrolizumab/combination treatment, administration of corticosteroids and/or other supportive care. For suspected irAEs, ensure adequate evaluation to confirm etiology or exclude other causes. Additional procedures or tests such as bronchoscopy, endoscopy, skin biopsy may be included as part of the evaluation. Dose modification and toxicity management guidelines for irAEs associated with pembrolizumab/combination treatment are provided in Table 3 below.

	5.2.2	
Deleted: The Pharmacy Manual contains specific instructions for the preparation of the pembrolizumab infusion fluid and administration of infusion solution.

	5.3.2.	
Added: Seasonal influenza vaccines for injection are generally killed virus vaccines and are allowed; however, intranasal influenza vaccines (eg, FluMist®) are live attenuated vaccines and are not allowed.

	5.4.1.	
Deleted references to the ECI guidance document.
 
Added: in Section 5.2.1.2, Table 3.
 
Changed Management of Infusion Reactions section to read: Dose modification and toxicity management of infusion-reactions related to pembrolizumab Pembrolizumab may cause severe or life-threatening infusion-reactions including severe hypersensitivity or anaphylaxis. Signs and symptoms usually develop during or shortly after drug infusion and generally resolve completely within 24 hours of completion of infusion. Dose modification and toxicity management guidelines on pembrolizumab associated infusion reaction are provided in Table 4.

	5.5.2.	
Deleted: Furthermore, it is not known if pembrolizumab has transient adverse effects on the composition of sperm.
 
Deleted: and male
 
Deleted: or impregnating a partner, respectively

	6.1	
Added: PD-L1 analysis during screening
 
Added: footnote 7Refer to the MISP Sample Handling Manual for collection and shipping instructions.

	7.1.2.1.	
Deleted: For subjects receiving treatment with pembrolizumab all AEs of unknown etiology associated with pembrolizumab exposure should be evaluated to determine if it is possibly an event of clinical interest (ECI) of a potentially immunologic etiology (termed immune-related adverse events, or irAEs); see the separate ECI guidance document regarding the identification, evaluation and management of potential irAEs.

	7.1.2.5.4.	
Added: iRECIST is based on RECIST 1.1, but adapted to account for the unique tumor response seen with immunotherapeutic drugs. iRECIST will be used by the investigator to assess tumor response and progression and make treatment decisions. When clinically stable, participants should not be discontinued until progression is confirmed per iRECIST.
 
Added: If repeat imaging does not confirm PD per iRECIST (below), as assessed by the Investigator, and the participant continues to be clinically stable, study treatment may continue and follow the regular imaging schedule
 
Added: Confirmation of Progression per iRECIST
 
Progression is considered confirmed, and the overall response will be confirmed progressive disease per iRECIST (iCPD), if ANY of the following occurs:
 
 
• Any of the factors that were the basis for the initial unconfirmed progressive disease (iUPD) show worsening 
 
o For target lesions, worsening is a further increase in the sum of diameters of <math>\geq 5</math> mm, compared to any prior iUPD time point
 
o For non-target lesions, worsening is any significant growth in lesions overall, compared to a prior iUPD time point; this does not have to meet the “unequivocal” standard of RECIST 1.1
 
o For new lesions, worsening is any of these: 
 
An increase in the new lesion sum of diameters by <math>\geq 5</math> mm from a prior iUPD time point
 
Visible growth of new non-target lesions
 
The appearance of additional new lesions
 
 
 
 
 
• Any new factor appears that would have triggered PD by RECIST 1.1
 

	7.2.	Changed the Worldwide Product Safety; FAX to [name]
	7.2.1.	Deleted: All reports of overdose with and without an adverse event must be reported within 24 hours to the Sponsor and within 2 working days hours to Merck Global Safety. (Attn: Worldwide Product Safety; [contact])
	7.2.3.1.	
Added: o Medical or scientific judgment should be exercised in deciding whether SAE reporting is appropriate in other situations such as important medical events that may not be immediately life-threatening or result in death or hospitalization but may jeopardize the participant or may require medical or surgical intervention to prevent 1 of the other outcomes listed in the above definition. These events should usually be considered serious.
 
o Examples of such events include invasive or malignant cancers, intensive treatment in an emergency room or at home for allergic bronchospasm, blood dyscrasias or convulsions that do not result in hospitalization, or development of drug dependency or drug abuse.
 
Deleted: Additionally, any serious adverse event, considered by an investigator who is a qualified physician to be related to Merck product that is brought to the attention of the investigator at any time outside of the time period specified

		
in the previous paragraph also must be reported immediately to the Sponsor and to Merck.
 
Deleted: recorded as such on the Adverse Event case report forms/worksheets and reported within 24 hours to the Sponsor (CINJ) and CINJ will report within 2 working days Global Safety. (Attn: Worldwide Product Safety; [contact])
 
Deleted: The trial site guidance for assessment and follow up of these criteria can be found in the Investigator Trial File Binder (or equivalent).
 
Deleted: 1.Additional adverse events: A separate guidance document has been provided entitled “Event of Clinical Interest Guidance Document” (previously entitled, “Event of Clinical Interest and Immune-Related Adverse Event Guidance Document”). This document can be found in Appendix 4 and provides guidance regarding identification, evaluation and management of ECIs and irAEs.
 
ECIs (both non-serious and serious adverse events) identified in this guidance document from the date of first dose through 90 days following cessation of treatment, or 30 days after the initiation of a new anticancer therapy, whichever is earlier, need to be reported within 24 hours to the Sponsor (CINJ) and CINJ will report within 2 working days to Merck Global Safety. (Attn: Worldwide Product Safety; [contact]), regardless of attribution to study treatment, consistent with standard SAE reporting guidelines.
 
Subjects should be assessed for possible ECIs prior to each dose. Lab results should be evaluated and subjects should be asked for signs and symptoms suggestive of an immune-related event. Subjects who develop an ECI thought to be immune-related should have additional testing to rule out other etiologic causes. If lab results or symptoms indicate a possible immune-related ECI, then additional testing should be performed to rule out other etiologic causes. If no other cause is found, then it is assumed to be immune-related.

	7.2.3.2.	
	10.6.1.	
Deleted: annual review
 
Added: quarterly review

	10.7.	
Added: This protocol is available at the Rutgers Cancer Institute of New Jersey (CINJ)/Robert Wood Johnson University Hospital (RWJUH) in New Brunswick and NYU Langone Health.

	11.3.2.	
Changed pulmonitis to pneumonitis

	11.4.	
Deleted entire section

	11.5.	
Changed the section numbering to 11.4 and subsections were updated to 11.4.1 – 11.4.3

19	2,3	16	Trial Diagram updated to reflect closure of arm 1

## 1.0 TRIAL SUMMARY

Abbreviated Title	Basket Trial of Pembrolizumab
Trial Phase	II
Clinical Indication	BRCA , POLE and POLD1 mutant tumors
Trial Type	Therapeutic
Type of control	None
Route of administration	IV
Trial Blinding	None
Treatment Groups	BRCA , POLE and POLD1 mutant tumors
Number of trial subjects	40
Estimated enrollment period	18-24 months
Estimated duration of trial	30-36 months
Duration of Participation	30-36 months

## 2.0 TRIAL DESIGN

### 2.1 Trial Design

This will be a phase II trial that will enroll two cohorts of patients: a) Patients with advanced solid tumors with *POLE* and *POLD1* mutations whose tumors exhibit a microsatellite stable phenotype and b) Patients with advanced solid tumors with *BRCA1/2* mutations. The primary endpoint will be response rate, which we anticipate to be higher than that seen historically in unselected solid tumors. Progression free survival will also be measured.

**Patient Selection and Recruitment:** Patients referred for this trial must submit pre-treatment tumor specimens for next generation sequencing analysis to characterize the presence of *POLE*, *POLD1*, or *BRCA1/2* mutations. Enrollment will be guided by presence of tumor mutations (as opposed to tumor histology). Patients with *BRCA1/2* mutations will be identified through standard of care testing for these mutations. If Foundation One next generation sequencing panel, or other similarly validated analysis, is ordered commercially prior to the patient's referral for study this analysis will be acceptable for enrollment to this protocol. Patients with *POLE/POLD1* mutations will likely be identified through Foundation One next generation sequencing panel, or other similarly validated analysis, ordered commercially prior to the patient's referral for study. This analysis will be acceptable for enrollment to this protocol. Tumors harboring hotspot mutations in *POLE/POLD1* that result in a hypermutator phenotype are expected to be microsatellite stable (MSS). Testing for microsatellite instability will be done in all *POLE* mutant cases prior to enrollment. Tumors harboring non-hotspot *POLE* or *POLD1* mutations that show clear evidence of MSI will be excluded.

[figure not shown]
Archived tumor tissue will be retrieved for correlative analyses from each patient (20 unstained slides preferred, minimum of 15 required). If inadequate archived tissue is available, a fresh tumor biopsy must be performed.

Mandatory tumor assessments include collection of archived or fresh tumor at baseline and a biopsy of tumor upon progression. Fresh tumor biopsies or archived tumor tissue will be collected at baseline as well as peripheral blood mononuclear cell (PBMC) samples. Patients will be treated with pembrolizumab dosed at 200 mg intravenous infusion every three weeks (1 cycle = 21 days). Patients will be evaluated for response by RECIST 1.1 and iRECIST criteria after every 9 weeks (3 cycles) of treatment until cycle 8, then subsequently after every 12 weeks (4 cycles) of treatment. PBMCs (tumor optional) will be sampled to assess treatment effect on the immune response at the following time points: baseline and after week 4 of pembrolizumab. Mandatory submission of PBMC tumor biopsies at progression will occur provided that the biopsy of the progressing tumor does not impose significant risk in the opinion of the investigator. Plasma samples for analysis of cell-free DNA will also be collected prior to initiation of treatment, and every 6 weeks of treatment. The above design and assessments are depicted in the schema below.

## 2.2

### 2.3 Trial Diagram

Arm 1 is closed

## 3.0 OBJECTIVE(S) & HYPOTHESIS(ES)

### 3.1 Primary Objective(s) & Hypothesis(es)

- Objective:** To evaluate the response rate of pembrolizumab in patients with evidence of genomic instability classified as follows: 1) All solid tumors with *POLE* and *POLD1* mutations 2) All solid tumors with *BRCA1/2* mutations

RUTGERS | eIRB  
APPROVED

IRB ID: Pro20170001392  
Approval Date: 2/22/2023  
Expiration Date: 5/10/2023

**Hypothesis:** Tumors with evidence of genomic instability such as those with mutations in *POLE*, *POLD1* and *BRCA1* and *BRCA2* will have higher response rates than tumors that do not exhibit these mutations.

### 3.2 Secondary Objective(s) & Hypothesis(es)

- (1) **Objective:** To compare the complete and partial response rate, and response durability (immune related progression free survival), to historical cohort information of unselected patients treated with pembrolizumab
- (2) **Hypothesis:** PFS rate will be improved in patients whose tumors have *POLE* and *POLD1* mutations, or *BRCA1/2* mutations, compared with unselected patients

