## **4.2.2 Rationale for Endpoints**

### **4.2.2.1 Efficacy Endpoints**

It has been published in a phase 2 trial of pembrolizumab that tumors with defects in mismatch repair deficiency have superior response rates and immune related progression free survival compared with tumors that are mismatch repair proficient. We similarly expect that tumors with *POLE*, *POLD1* and *BRCA1/2* mutations will have superior response rates and progression free survival compared with cohorts of patients whose tumors are not selected for genomic instability. We have thus selected the primary clinical endpoint of response rate and secondary endpoints of immune related progression free survival to be evaluated in this basket trial.

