#### **7.1.2.5.6 Determining the date of progression or response**

For all patients who experience disease progression on study, the date noted for disease progression is the time of the scan when it was originally determined, and not the later date of the confirmatory scan.

For all patients who experience complete or partial response on study, the date noted for disease response is the time of the scan when it was originally determined, and not the later date of the confirmatory scan.

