## 8.0 STATISTICAL ANALYSIS PLAN

Sample size justification. To address the primary objective, we have calculated the 95% confidence intervals (CI's) to assess precision of expected response rate of pembrolizumab in treating patients with specified mutant tumors (e.g., *POLE*, *POLD1*, and *BRCA1* and 2). Responses to single agent PD-1 inhibition are not seen in the majority of patients; available published data in pretreated triple negative breast, lung, ovarian tumors, histologies likely to be enrolled to this trial, have ranged from 11-19% in small studies. Based on the data in MSI high tumors by Le et al, responses can be expected to rise significantly in tumors with genomic instability, with the lowest rate of 40% in their published series. We thus assume that the response rate of pembrolizumab in our trial, treating patients with *POLE* (or *POLD1*) and/or *BRCA1/2* mutant tumors, will similarly be at about 40%. For n=23 patients for each type of tumors ([*POLE* or *POLD1*] and [*BRCA1* and 2]), we expect to yield a 95% CI of (0.20, 0.60), within the 40%+/- 20% range (Table 7). This confidence interval is above the response rate of using standard therapy in treating unselected cancer patients suggesting significant improvement of pembrolizumab over standard therapies.

To address the secondary objective, we used the same 95% CI calculations (Table 7), assuming no loss of follow-up, to assess the precision of expected PFS rate of pembrolizumab at 6 months in treating patients with specified mutant. Based on the data in Le et al (Panel C Fig 2), the PFS rate at 6 months was at least 35% while the immune-related PFS at 20 weeks was at least 67%. Assuming the 6-month PFS rates in our study will be similarly at least 35%. With n=23 patients for each type of tumors ([*POLE* or *POLD1*] and [*BRCA1* and 2]), we expect to yield a 95% CI of (0.15,0.55) for PSF of 35% and (0.46,0.84) for PSF of 65%, both within the +/- 20% range.

**Table 7. 95% Confidence Intervals for Response and/or PFS\* Rate Based on Estimated Rate (P) and Sample Size (n) for a Specific Mutant Tumor.**

P							
n	0.25	0.30	0.35	0.40	0.50	0.65	0.75
20	(0.06,0.44)	(0.10,0.50)	(0.14,0.56)	(0.18,0.62)	(0.28,0.72)	(0.44,0.86)	(0.56,0.94)
23	(0.07,0.43)	(0.11,0.49)	(0.15,0.55)	(0.20,0.60)	(0.29,0.71)	(0.46,0.84 )	(0.57,0.93)

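### Section 3.2 equates response durability with immune-related PFS, and 8.0 plans only a 6-month PFS proportion in the whole cohort; neither identifies how long responses last.

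*Combined protocol and SAP*

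**What the plan says.** - **Objective (3.2).** The secondary objective compares response rates and durability with historical unselected patients. Durability is given as "response durability (immune related progression free survival"). The paired hypothesis concerns patients with the mutations, not responders: "PFS rate will be improved in patients whose tumors have" the named mutations.
- **Endpoint rationale (4.2.2.1).** It lists "secondary endpoints of immune related progression free survival to be evaluated in this basket trial" and does not mention duration of response.
- **Analysis (8.0).** The response rate is sized "For n=23 patients for each type of tumors" and is assumed "will similarly be at about 40" percent. The secondary objective uses the same n and the same interval method, "to assess the precision of expected PFS rate of pembrolizumab at 6 months". The assumed rates come from a cited trial in which "the PFS rate at 6 months was at least 35% while the immune-related PFS at 20 weeks was at least 67" percent.
- **Dating rule (7.1.2.5.6).** For responders, "the date noted for disease response is the time of the scan when it was originally determined"; progression is likewise dated to the scan that first showed it.
- **Scan schedule (6.1, footnote 3).** Imaging is due before Cycles 4 and 7, then before Cycles 11, 15, 19 and so on, with 3-week cycles.

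**The concern.** Durability of response is a property of responders: how long a response lasts once it has begun. PFS covers the whole cohort, including patients with no response to lose. Three quantities therefore stand for one aim: durability in the objective, immune-related PFS in its gloss and in 4.2.2.1, and a 6-month PFS proportion in the analysis section. If the last is all that is produced, the durability part of objective 3.2 goes unanswered. The same PFS figure could accompany responses that nearly all last or responses that nearly all fail early.

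**Working it through.** **Inputs.** From 8.0: n = 23 per tumor type, response rate 40%, 6-month PFS 35% (65% is also tabulated), no loss to follow-up. From 6.1: the scan schedule. That PFS is taken over all 23 patients is an inference from the usual meaning of PFS and from the shared n; 3.2 does not say so.

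**1. Reproducing the plan's intervals.** Wald interval, p ± 1.96 × √(p(1 − p)/23):

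| p | Computed | Stated in 8.0 |
|---|---|---|
| 0.35 (PFS) | 0.155 to 0.545 | 0.15 to 0.55 |
| 0.65 (PFS) | 0.455 to 0.845 | 0.46 to 0.84 |
| 0.40 (response) | 0.200 to 0.600 | 0.20 to 0.60 |

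All agree within 0.01. The planned secondary statistic is thus a simple proportion of 23.

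**2. What that proportion says about responders.** Let S_R and S_N be the shares of responders and non-responders progression-free at 6 months. Then

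PFS(6 months) = 0.40 × S_R + 0.60 × S_N.

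- At PFS = 0.35, S_N = 0 gives S_R = 0.35/0.40 = 0.875. S_R = 0 gives S_N = 0.35/0.60 = 0.583. So S_R can lie anywhere from 0% to 87.5%.
- At PFS = 0.65, S_N = 1 gives S_R = (0.65 − 0.60)/0.40 = 0.125. S_R = 1 gives S_N = (0.65 − 0.40)/0.60 = 0.417. So S_R runs from 12.5% to 100%.

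In whole patients, with 9 responders and 14 non-responders, 8 of 23 progression-free (35%) could be 8 of 9 responders and no non-responder, or no responder and 8 of 14 non-responders. These are algebraic limits. The extremes are unlikely, but nothing in the planned analysis says where between them the truth lies.

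**3. What the 6-month horizon can show.** Cycle 4 starts 3 × 3 = 9 weeks after the first dose, Cycle 7 at 6 × 3 = 18 weeks and Cycle 11 at 10 × 3 = 30 weeks. Six months is about week 26. A response first seen at week 9 has had one later scheduled scan by then; one first seen at week 18 has had none. Section 7.1.2.5.5 also lets confirmation of response wait for the next scheduled scan. Even if S_R were known exactly, it would not separate responses lasting a few months from those lasting two years.

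**4. Do non-responders drive the figure?** At 35% PFS, 23 × 0.65 = 14.95 events are expected by 6 months, among 9.2 responders and 13.8 non-responders.

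- Fewest events from non-responders: 14.95 − 9.2 = 5.75, or 38%.
- Most: 13.8, or 92%.
- If half the responders are progression-free, S_N = (0.35 − 0.20)/0.60 = 0.25, and the non-responders' share is 0.60 × 0.75/0.65 = 69%.

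**5. Precision of a responder-only estimate.** Expected responders: 0.40 × 23 = 9.2. The Wald half-width at 50% is 1.96 × √(0.25/9.2) = 0.32, against 0.20 with n = 23. Exact 95% intervals are 0.21 to 0.86 for 5 of 9 and 0.30 to 0.93 for 6 of 9.

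**The case against.** The best defense is that the endpoint was chosen for a reason. The objective is a historical comparison, and 4.2.2.1 selects response rate and immune-related PFS because the cited mismatch-repair trial reported them. About 9 responders could not support such a comparison on duration of response. The parenthesis in 3.2 also tells the reader what is measured, and response and progression dates will be on file, so duration could be derived later.

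Much of this stands. It justifies keeping PFS and treating duration of response as descriptive. It does not make PFS a measure of durability, and leaving the derivation for later would mean choosing the confirmation and censoring rules after the data are seen.

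A reader might go further in three ways that the documents do not support:

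- **That the figure is driven by non-responders.** This is likely, but not forced: they could supply as few as 38% of the 6-month events.
- **That median PFS would be the same whether responses last 6 or 24 months.** Section 8.0 plans no median. Responders do move the planned proportion: if all 14 non-responders progress by 6 months, it still ranges from 0/23 to 9/23 = 39%.
- **That the trial would publish a number labeled durability.** Section 8.0 and Table 7 call the quantity PFS; the durability wording for this endpoint is confined to the objective in 3.2.

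**Conclusion.** The point holds as an endpoint-definition error. Objective 3.2 names durability, and neither its gloss nor the analysis in 8.0 measures it. At the plan's assumptions the 6-month PFS proportion leaves the responders' progression-free share open from 0% to 87.5% (12.5% to 100% at 65% PFS), and its horizon is too short to distinguish brief from lasting responses. The non-identification does not depend on how events split by response. It rests on reading PFS as a whole-cohort measure and on the 40% response rate; another rate changes the limits, not the conclusion.

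The switch between immune-related PFS (3.2, 4.2.2.1) and PFS (8.0) is a separate naming inconsistency that the same edit can settle. The consequence is modest: one secondary aim is affected.

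**What to change.** 1. In 3.2 and 8.0, define response durability as duration of response among confirmed responders, estimated descriptively by Kaplan-Meier from the first scan showing the later-confirmed CR or PR to progression or death.
2. Take progression from the trial's modified RECIST 1.1 (7.1.2.5.2 and 11.3), which requires PD to be confirmed, and date it to the first PD scan as in 7.1.2.5.6. Censor at the last assessment before new anticancer therapy.
3. Keep PFS as a separate whole-cohort secondary endpoint under its own name. Choose either PFS or immune-related PFS and use that criterion in 3.2, 4.2.2.1 and 8.0.

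The cost is SAP wording and one more curve from dates already recorded, with no added scans, visits or patients. The drawback is imprecision: with about 9 responders per cohort the estimate is descriptive and should not carry the historical comparison.
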